1.0 EXECUTIVE SUMMARY

Study Design

This is a placebo controlled study in 400 patients, testing the hypothesis that pre-treatment use of intravenous nitroglycerin will decrease the incidence of renal insufficiency after percutaneous angiography, cardiac or lower extremity

Intervention

Patients undergoing percutaneous angiography will be randomly assigned to receive intravenous nitroglycerin (5 mcg/min, titrated up to 50mcg/min for at least 1 hour, maintaining systolic blood pressure (BP) > 100 mmHg, before and 3 hours after the procedure) or a normal saline placebo in a 1:1 ratio.

Enrollment period

The patients will be enrolled during a 2 year period.

Rationale for this study

Animal models suggest that the impaired synthesis of nitric oxide is one important contributor to the pathogenesis of the vasoconstriction caused by exposure to contrast-media. Our previous, retrospective, pilot study supported the hypothesis that the administration of nitrates, particularly intravenous nitroglycerin, before PCI, may decrease the incidence of contrast induced nephropathy (CIN).

Primary Endpoint:

- 1- The primary endpoint will be the change in estimated glomerular filtration rate (eGFR) assessed by modification of diet for renal disease formula, after percutaneous angiography.

Secondary Endpoints:

- 1- CIN will be defined as an increase in serum creatinine of 25% or ≥ 0.5 mg/dl post-percutaneous angiography.
- 2- Safety profile of the intervention including volume overload, hypotension, headache, the need for hemodialysis, intra-aortic balloon pump, endotracheal intubation or the use of pressors.
- 3- Analysis and comparison to a CIN predictive score calculator (Mehran Score).

2.0 BACKGROUND

2.1 INTRODUCTION

CIN is a complication of percutaneous angiography that, when it occurs, usually begins shortly after the administration of contrast media (1-3). The incidence has been reported in the range of 0 to 50%, depending on comorbidities and risk factors (4-8). CIN usually resolves spontaneously, but it has been associated with an increased risk of morbidity, in-hospital death, and late mortality (9-10). There is no specific management for renal insufficiency after the development of CIN. Therefore, there is interest in finding preventive strategies. Available evidence supports the use of hydration, sodium bicarbonate, and reduction of contrast volume administered to patients at risk (22). Statin use for prevention of CIN is still controversial (30-32), with a recent publication showing promising results (33). A hydration system was proposed by Briguori et al. (34) that showed CIN preventive effects. Further studies are needed to support these findings. Other agents, such as N-acetylcysteine, fenoldopam, nifedipine, captopril, prostaglandins and aminophylline have been evaluated in the prevention of CIN with varying results (23-29).

Animal models suggest that the impaired synthesis of nitric oxide is one important contributor to the pathogenesis of the vasoconstriction that may lead to CIN (11-13). We plan to investigate whether the use of intravenous nitroglycerin before exposure to contrast media reverses this vasoconstriction, and therefore, prevents the development of CIN.

The present manuscript describes the background, rationale, study design, safety monitoring, and analysis plan for the proposed contrast nephropathy and nitrates trial (CoNaN).

2.2 CONTRAST-INDUCED NEPHROPATHY AND NITRIC OXIDE

The pathophysiology behind CIN is not well understood. Different mechanisms have been proposed to explain the decrease in glomerular filtration rate after exposure to contrast media. The two major theories for the development of CIN are renal vasoconstriction resulting in medullary hypoxemia, and direct cytotoxic effects of the contrast agents (14-18).

Devrim et al, performed a randomized animal model trial, exposing rat kidneys to contrast media and measuring nitric oxide (NO) levels after exposure. They suggested that non-ionic low osmolar contrast medium administration leads to accelerated oxidant reactions and decreased NO level in rat kidney tissues. (13)

In another animal model completed by Brezis et al. they exposed anesthetized rats to the inhibitor of NO formation, L-NG-monomethylarginine (LNMMA). While increasing blood pressure and reducing renal blood flow they measured a decline in oxygen tension. These responses were promptly reversed by L-arginine, a NO donor, which bypasses the LNMMA blockade. They concluded that vasodilatation by nitroglycerin may participate in the balance of

renal medullary oxygenation and play an important role in the prevention of medullary hypoxic injury. (19)

Agmon et al, produced a simple model of radiocontrast induced nephropathy. Rats were pretreated with indomethacin (prostaglandin blocker) and N omega-nitro-L-arginine methyl ester (L-NAME, to inhibit nitric oxide synthesis) and then exposed to a contrast agent. Acute renal failure consistently developed, with a decline in creatinine clearance. Pretreatment with L-NAME or indomethacin reduced basal medullary blood flow. It was concluded that prostanoids and nitric oxide have an important protective role in the renal response to radiocontrast material, and reduced synthesis of these vasoactive substances in renal/vascular diseases may predispose patients to radiocontrast nephropathy. (11)

The mechanism by which N-acetylcysteine and other antioxidants have been proposed to confer renal protection in some animal models and human trials is through stimulation of nitric oxide synthase (NOS) to increase the endothelial production of NO. (17)

Nitroglycerin exerts its effects by bypassing the NOS mechanism and forming nitric oxide. In smooth muscle, nitric oxide activates guanylate cyclase which increases guanosine 3'5' monophosphate (cGMP) leading to dephosphorylation of myosin light chains and smooth muscle relaxation. It produces a vasodilating effect on the peripheral veins and arteries, with more prominent effects on veins than arteries. (20)

In the study of Efrati et al, the administration N-acetylcysteine was associated with maintenance of higher urinary NO levels after exposure to contrast media in comparison to the placebo group, where it was associated with a decrease of NO urinary levels after exposure to the toxin. They explained that “contrast media agents can cause a direct tubular injury, leading to the generation of oxygen free radicals, which in turn react with nitric oxide to produce peroxynitrite. Peroxynitrite is a potent oxidant that further decreases nitric oxide bioavailability and results in more tissue injury. Patients with chronic renal failure, diabetes mellitus, and heart failure have impaired nitric oxide activity, which could account for their susceptibility to develop contrast media nephrotoxicity”. (17)

We recently completed a small retrospective study at our institution (exhibit A). We sought to investigate whether the use of nitrates before PCI reduces the incidence of CIN. We evaluated patients that were admitted to the hospital after PCI and had repeat serum creatinine measured. We measured the effects of pre-procedure nitrate use on post-PCI renal function in patients who received nitrates within 24 hours before the procedure and compared it with that of those who did not receive nitrates. Multivariable logistic regression analysis demonstrated that the use of nitrates correlated with a decrease incidence of CIN. Intravenous nitroglycerin infusion was associated with a lower risk of CIN compared with other means of administering nitrates. We concluded that the study supported the hypothesis that the administration of pre-PCI nitrates, particularly intravenous nitroglycerin, may decrease nephrotoxicity caused by contrast-media. But prospective, randomized-controlled trials are warranted to support or refute this hypothesis.

The mechanistic hypothesis of the CoNaN trial is that by pre-treating with intravenous nitroglycerin and exposing the renal vasculature to nitric oxide donor (NO), the damage caused by renal vasoconstriction and hypoxia due to radiographic contrast agent will be ameliorated, thus reducing the incidence of CIN.

2.3 NITROGLICERYN TO PREVENT CONTRAST INDUCED NEPHROPATHY

Experimental animal studies provide evidence that NO plays a role in CIN. The clinical information on the use of intravenous nitroglycerin to prevent CIN is limited to one retrospective study. Our hypothesis that pre-PCI exposure to intravenous nitroglycerin could prevent CIN has a favorable theoretical basis. The reality of our premise is still uncertain.

Our proposal for a randomized clinical trial will answer a simple clinical question. It will help to demonstrate a correlation or not, between experimental results obtained in animal models and human subjects. It will also contribute to clarify the role of NO donors in the renal vasculature.

3.0 INVESTIGATORS AND FACILITIES

3.1 STUDY LOCATION

The CoNaN trial will be performed at Mount Sinai Medical Center in Miami Beach, Florida. The Departments involved in the developing of the trial include: the Columbia University Division of Cardiology, the Division of Nephrology and the Department of Medicine.

3.2 STUDY MANAGEMENT

The trial will be coordinated by the CoNaN Trial research teams that consist of the principal and co-principal investigators, sub-investigators, and a study coordinator. The study coordinator will evaluate eligibility; obtain consent, schedule subject's follow-up visits, data collection and maintenance of study documentation. Handling of investigational products will be the responsibility of an onsite pharmacist as well as the assistant investigators.

3.2.3 INDEPENDENT DATA AND SAFETY MONITORING COMMITTEE

The DSMB will be composed of experts not associated with the trial. The Chair and members are: [name] MD (Chair), [name] MD and [name] MD (Nephrologist). They will review unblinded data, and obtain statistical consultation as needed.

The first data monitoring will occur once 100 patients have been enrolled. After the first visit has been completed, monitoring visits frequency will be every 12 months, depending on enrollment

4.0 CONAN TRIAL DESIGN

The Contrast Nephropathy and Nitrates trial (CoNaN) is a single center, randomized, 1 x 1 factorial clinical trial designed to test the effects of intravenous nitroglycerin infusion in renal function given prior to angiography.

Specific aims for this trial include:

- To determine whether the intravenous nitrates have any effect on the glomerular filtration rate (GFR) after the exposure to contrast media.
- To determine if intravenous nitroglycerin will decrease the incidence of CIN.

4.1 PRIMARY ENDPOINT

The primary endpoint for this trial will be to determine the change in glomerular filtration rate after exposure to contrast media. We will compare the change in GFR before and after percutaneous angiography of the group that received intravenous nitroglycerin with the change in GFR before and after percutaneous angiography of the group that did not receive intravenous nitroglycerin.

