4.1.1 GLOMERULAR FILTRATION RATE

We will estimate the GFR using the modification of diet in renal disease (MDRD) formula:

$$\text{GFR} = 175 \times \text{SerumCr}^{-1.154} \times \text{age}^{-0.203} \times 1.212 \text{ (if patient is African American)} \times 0.742 \text{ (if female)}$$

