4.2.1 MEHRAN SCORE

According to a validated score proposed by Mehran et al. patients with a score equal or greater than 6, has a 14% chances or more of developing CIN (21). We will use this value to recruit patients with a high probability of developing CIN. The score will be calculated using the following variables: hypotension (5 points for BP $<80/60$ mmHg), intra-aortic balloon pump use before during or after the procedure (5 points), congestive heart failure (5 points for New York Heart Association Class II-III, history of pulmonary edema or an ejection fraction $<40\%$) age >75 years (4 points), anemia (3 points for hematocrit $<39\%$ for men and $<35\%$ for women), diabetes mellitus (3 points), serum creatinine >1.5 (4 points), GFR <60 (2 points for 41-60; 4 points for 21-40 and 6 points for <20) and contrast volume used (1 for each 100 cc).

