5.2.2 INCLUSION CRITERIA

All of the following inclusion criteria must be present for the patient to be enrolled in the trial.

- 1- Patient must be scheduled for percutaneous angiography, defined as diagnostic cardiac catheterization, or lower extremity or aortic iodinated contrast angiography.
- 2- Patients must have a Mehran score of at least 6 before the procedure.
- 3- Patients must have baseline creatinine and hemoglobin drawn before the procedure.
- 4- Signed informed consent.

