5.2.3 EXCLUSION CRITERIA

None of the following exclusion criteria must be present for the patient to be enrolled in the trial

- 1- Patients on renal replacement therapy before randomization, will be excluded.
- 2- Being exposed to any types of nitrates 48 hours prior to randomization,
- 3- History of allergic reaction to any of the components of intravenous nitroglycerin.
- 4- Exposure to contrast media 4 days prior randomization.
- 5- Planned revascularization in the next 24 to 48 hours of the first PCI procedure.
- 6- The patient is hypotensive (<90/60mmHg) at the time of randomization.
- 7- Patients exposed to phosphodiesterase inhibitors 48 hours prior to randomization

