5.2.4 SCREENING AND BASELINE EVALUATION

Potentially eligible patients will undergo an initial evaluation in which eligibility will be confirmed and the trial protocol explained in detail. All willing and eligible patients providing informed consent will have baseline data obtained including relevant history and use of all conventional and alternative therapies. Baseline laboratory tests will be performed and information on quality of life will be obtained.

The following variables will be obtained for all patients included in the trial: age, gender, weight, height, body mass index, blood pressure, left ventricular ejection fraction, hypertension, diabetes mellitus, peripheral vascular disease, medication use (angiotensin converting enzyme inhibitors, calcium channel blockers, beta blockers, statins, ascorbic acid, acetylcysteine, angiotensin receptor blockers, diuretics, aspirin), PCI (number of vessels) smoking status, amount of contrast, type of contrast, amount of hydration, serum hemoglobin, serum sodium, serum potassium, baseline creatinine and post procedure creatinine, glomerular filtration rate.

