5.2.5 RANDOMIZATION

After inclusion and exclusion criteria verification, coordinator will complete the randomization screen, in the system. The patients will be randomly assigned to one of the two treatment arms. The coordinator will order the treatment in the patient's chart and start the pre-stocked infusion. The infusions will consist in intravenous nitroglycerin in addition to Intravenous Saline or Intravenous saline.

We will randomize using a computer generated pre-set list. The computer program will randomly assign a letter (A or B) to each individual case up to 400 cases. The trial coordinator and the pharmacist will be the only un-blinded persons that will have access to the randomization list. In case that for safety reasons an investigator must know if the patient is receiving the experimental therapy or not, a copy of the randomization list will be held at the coordinator's office.

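### The primary comparison of eGFR change specifies no adjustment for baseline eGFR; prespecifying ANCOVA costs almost nothing and gains between nothing and a moderate amount of precision.

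*Combined protocol and SAP*

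**What the plan says.** The executive summary (section 1.0) states: "The primary endpoint will be the change in estimated glomerular filtration rate (eGFR) assessed by modification of diet for renal disease formula". Section 4.1 gives the only account of how the arms will be compared: "We will compare the change in GFR before and after percutaneous angiography of the group that received intravenous nitroglycerin", set against the corresponding change in the group not given nitroglycerin. Section 4.1.1 adds the formula: "We will estimate the GFR using the modification of diet in renal disease (MDRD) formula". No section names a test, a model or a covariate for this comparison.

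The covariate will be available. Section 5.2.2 requires it for entry: "Patients must have baseline creatinine and hemoglobin drawn before the procedure". Section 5.2.4 lists, for all patients, "baseline creatinine and post procedure creatinine, glomerular filtration rate".

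The design is not stated to balance renal function. Section 5.2.5 says only "We will randomize using a computer generated pre-set list", with no stratification factor.

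Entry allows a wide range of baseline renal function. The only renal exclusion in section 5.2.3 is "Patients on renal replacement therapy before randomization, will be excluded". The Mehran score in section 4.2.1 awards GFR points as "2 points for 41-60; 4 points for 21-40 and 6 points for <20". Yet the qualifying score of 6 can be reached with no renal points at all, for example anemia (3) plus diabetes (3).

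**The concern.** A change score fixes the coefficient of baseline at 1, whereas ANCOVA estimates it from the data. If the true slope of post-procedure on baseline eGFR is not 1, the change score remains correlated with baseline. Two things follow.

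- **Precision.** The unadjusted comparison carries baseline variation that could be removed with data already in hand.
- **Chance imbalance.** If one arm happens to start with higher eGFR, the change-score difference is biased conditional on that imbalance. Simple randomisation with no stated stratification does nothing to limit this.

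Baseline is likely to matter here because of how the outcome is scaled. Under the MDRD formula, a given percentage rise in creatinine is a fixed percentage fall in eGFR, so the absolute fall depends on where the patient starts.

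The plan's silence also allows adjusted and unadjusted results both to be produced, and one of them to be preferred once the data are known.

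**Working it through.** **Inputs.** From the documents: 400 patients randomised 1:1 (sections 5.1 and 5.2.1), so 200 per arm, and the MDRD creatinine exponent of −1.154 (section 4.1.1). The only power calculation, in section 5.1, concerns a binary failure rate of 0.30 against 0.15. Its 161 per arm reproduces exactly (two-sided, pooled variance, no continuity correction), but it supplies no SD, correlation or target difference for eGFR. The following are therefore **assumptions**: ρ, the correlation between baseline and post-procedure eGFR, and k, the ratio of post-procedure to baseline SD.

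**Step 1: scale of the outcome.** A 25% rise in creatinine multiplies eGFR by 1.25^(−1.154) = 0.773, a fall of 22.7%. That is 0.227 × 20 = 4.5 mL/min at eGFR 20 and 0.227 × 60 = 13.6 mL/min at eGFR 60.

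**Step 2: relative precision.** Set the baseline SD to 1 and the post-procedure SD to k. Per patient:

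- Var(change) = 1 + k² − 2ρk
- Var(ANCOVA) = k²(1 − ρ²)

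For k = 1 and ρ = 0.7 these are 0.60 and 0.51, and 0.51/0.60 = 0.85. The ratio ANCOVA/change over a grid:

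| k | ρ = 0.7 | ρ = 0.8 | ρ = 0.9 |
|---|---|---|---|
| 0.8 | 0.628 | 0.640 | 0.608 |
| 0.9 | 0.751 | 0.788 | 0.810 |
| 1.0 | 0.850 | 0.900 | 0.950 |
| 1.1 | 0.921 | 0.968 | 1.000 |
| 1.2 | 0.966 | 0.997 | 0.977 |

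At k = 1 the ratio reduces to (1 + ρ)/2. Simulation at 200 per arm (3,000 runs per ρ) agreed closely, giving 0.832, 0.893 and 0.955 for ρ = 0.7, 0.8 and 0.9. Multiplying by 400 gives about 340, 360 and 380 patients in place of 400. For k from 0.9 to 1.1 the range is about 300 to 400. At ρ = 0.95 and k = 1 the ratio is 0.975. The ratio is exactly 1 when the slope ρk = 1, for example ρ = 0.9 and k = 1.11.

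**Step 3: cost of adjusting.** The finite-sample variance factor for one covariate is 1 + 1/(400 − 4) = 1.0025, about 0.25%.

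**Step 4: conditional type I error of the change-score test.** The SE of the baseline difference is √(2/200) = 0.1 SD. Given an imbalance d, the bias is (ρk − 1)d. The test statistic then has mean (bias)/SE(change) and SD equal to the square root of the variance ratio. For k = 1, ρ = 0.7 and d = 0.2:

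- bias = −0.3 × 0.2 = −0.06
- SE(change) = √(0.60 × 2/200) = 0.0775
- mean z = −0.775, SD = √0.85
- P(|z| > 1.96) = 0.101

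| Imbalance (k = 1) | ρ = 0.7 | ρ = 0.8 | ρ = 0.9 |
|---|---|---|---|
| One SE (0.1 SD) | about 5.0% | about 5.0% | about 5.0% |
| Two SE (0.2 SD) | 10.1% | 8.4% | 6.7% |

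An imbalance of two SE or more arises in about 5% of randomisations. With no imbalance the rate is below 5% (about 3.4% at ρ = 0.7), and averaged over randomisations it is 5%. At slope 1 it is 5% throughout.

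**The case against.** The strongest reply is that the plan is silent rather than wrong. Section 4.1 describes an endpoint, and ANCOVA of the change on baseline would be compatible with it. The larger gap is that no analysis method at all is given for the primary endpoint. That is fair: the unadjusted comparison is the literal reading of section 4.1, not a stated method. But the silence leaves the choice open, which is a reason to name the covariate.

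Second, the unadjusted comparison is valid, and the conditional error rates above do not show an inflated error rate for the trial. This stands in full. They describe what happens in an unlucky randomisation and are offset by rates below 5% when the arms are well balanced.

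Third, the gain rests entirely on assumed inputs and may be small. The lowest ratios (k = 0.8 or 0.9) need the eGFR SD to shrink after contrast, and the documents give no reason to expect that. Where change is proportional to baseline, much of the effect is unequal variance, which a linear baseline term does not remove. A simulation of that mechanism (baseline mean 55, SD 15–25; mean fall 2–10%; SD of the fall 10–20 percentage points) gave variance ratios of 0.86 to 1.00, at least 0.93 in 24 of 27 settings. It added no separate measurement error, which would raise the gain somewhat. This part stands as a caution on size. It does not reverse the trade: the possible loss is about 0.25% of variance.

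The patient equivalents also assume that all 400 patients provide a post-procedure creatinine. Section 5.3 relies on discharged patients returning at 48 hours, and no dropout rate is stated.

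**Conclusion.** The concern holds. No baseline adjustment is specified for the primary comparison, although the covariate is mandatory for entry and is needed to form the change score in the first place. The omission does not bias the randomised comparison or raise its overall type I error. It forgoes precision and leaves an analytic choice open.

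The size is illustrative only. With equal SDs and a correlation of 0.7 to 0.9, the variance saving is 15% down to 5%. Allowing k from 0.9 to 1.1, it runs from 25% to nil. The k = 0.8 and 1.2 rows show sensitivity and should not be taken as expected values. Confidence is high that the omission exists and that adjusting is the better choice; it is low for any single figure for the gain. This is a change the sponsor should make, not a flaw that invalidates the trial.

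**What to change.** In section 4.1, prespecify the primary analysis as a linear model (ANCOVA) of post-procedure eGFR on treatment arm with baseline eGFR as covariate. Modelling the change instead gives the same treatment effect. Report the adjusted mean difference between arms with its 95% confidence interval.

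Keep the eGFR scale for the primary analysis, because sections 1.0 and 4.1 define the endpoint as change in eGFR. Add the same model on log eGFR as a prespecified sensitivity analysis: on that scale a given percentage rise in creatinine counts equally at every baseline, which addresses the scale issue in step 1.

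The cost is one or two sentences and one degree of freedom. No extra data, patients or procedures are needed. The text should be in place before any unblinded comparison of the primary endpoint.
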